#### [name]

- j. Metformin 2550 mg + glibenclamide 5 mg  $\rightarrow$  metformin 2550 mg + glibenclamide 2.5 mg
- k. Metformin 2550 mg + glibenclamide 10 mg  $\rightarrow$  metformin 2550 mg + glibenclamide 5 mg
- I. Metformin 2550 mg + glibenclamide 15-20 mg → metformin 2550 mg + glibenclamide 10 mg
- 13. Taking metformin and glibenclamide, with hypoglycemia or hypoglycemia symptoms, problems with metformin
  - a. Agrees to take metformin
    - i. Metformin 500-850 mg + glibenclamide 2.5 mg  $\rightarrow$  metformin 850 mg
    - ii. Metformin 500-850 mg + glibenclamide 5 mg  $\rightarrow$  metformin 850 mg + glibenclamide 2.5 mg
    - iii. Metformin 500-850 mg + glibenclamide 10 mg  $\rightarrow$  metformin 850 mg+ glibenclamide 5 mg
    - iv. Metformin 500-850 mg + glibenclamide 15-20 mg → metformin 850 mg + glibenclamide 10 mg
  - b. Refuses to take metformin
    - i. Metformin 500-850 mg + glibenclamide 2.5 mg  $\rightarrow$  stop medications, recheck A1c in 3 months
    - ii. Metformin 500-850 mg + glibenclamide 5 mg  $\rightarrow$  glibenclamide 2.5 mg
    - iii. Metformin 500-850 mg + glibenclamide 10 mg  $\rightarrow$  glibenclamide 5 mg
    - iv. Metformin 500-850 mg + glibenclamide 15-20 mg  $\rightarrow$  glibenclamide 10 mg
  - c. Metformin 1000-1700 mg + glibenclamide 2.5 mg  $\rightarrow$  metformin 850 mg
  - d. Metformin 1000-1700 mg + glibenclamide 5 mg  $\rightarrow$  metformin 850 mg + glibenclamide 2.5 mg
  - e. Metformin 1000-1700 mg + glibenclamide 10 mg  $\rightarrow$  metformin 850 mg + glibenclamide 5 mg
  - f. Metformin 1000-1700 mg + glibenclamide 15-20 mg  $\rightarrow$  metformin 850 mg + glibenclamide 10 mg
  - g. Metformin 2000-2550 mg + glibenclamide 2.5 mg  $\rightarrow$  metformin 1700 mg
  - h. Metformin 2000-2550 mg + glibenclamide 5 mg → metformin 1700 mg + glibenclamide 2.5 mg
  - i. Metformin 2000-2550 mg + glibenclamide 10 mg → metformin 1700 mg + glibenclamide 5 mg
  - j. Metformin 2000-2550 mg + glibenclamide 15-20 mg  $\rightarrow$  metformin 1700 mg + glibenclamide 10 mg

#### Tx goal< A1c <9

- Not taking medications or nonadherent, no hypoglycemia or hypoglycemia symptoms, no problems with metformin → metformin 1700 mg
- 2. Not taking medications or nonadherent, no hypoglycemia or hypoglycemia symptoms, problems with metformin
  - a. Agrees to take metformin  $\rightarrow$  metformin 850 mg + glibenclamide 2.5 mg
  - b. Refuses to take metformin  $\rightarrow$  glibenclamide 2.5 mg
- 3. Not taking medications or nonadherent, hypoglycemia or hypoglycemia symptoms → metformin 1700 mg
- 4. Not taking medications or nonadherent, hypoglycemia or hypoglycemia symptoms, problems with metformin
  - a. Agrees to take metformin  $\rightarrow$  metformin 850 mg
  - b. Refuses to take metformin, prescribed glibenclamide >2.5 mg  $\rightarrow$  glibenclamide 2.5 mg
  - c. Refuses to take metformin, prescribed glibenclamide 2.5 mg  $\rightarrow$  MD consult
- 5. Taking metformin without problems
  - a. Metformin 500-1000 mg  $\rightarrow$  metformin 1700 mg
  - b. Metformin 1500-2000 mg → metformin 2550 mg
  - c. Metformin 2550 mg  $\rightarrow$  metformin 2550 mg + glibenclamide 2.5 mg
- 6. Taking metformin with problems
  - a. Metformin 500-850 mg, agrees to take metformin → metformin 850 mg + glibenclamide 2.5 mg

[name]

- b. Metformin 500-850 mg, refuses to take metformin  $\rightarrow$  glibenclamide 2.5 mg
- c. Metformin 1000-1700 mg  $\rightarrow$  metformin 850 mg + glibenclamide 2.5 mg
- d. Metformin 2000-2550 mg  $\rightarrow$  metformin 1700 mg + glibenclamide 2.5 mg
- 7. Taking glibenclamide without problems
  - a. Glibenclamide 2.5-10 mg  $\rightarrow$  metformin 1700 mg + glibenclamide current dose
  - b. Glibenclamide 15-20 mg → metformin 1700 mg + glibenclamide 10 mg
- 8. Taking glibenclamide, previous problems with metformin
- a. Agrees to take metformin
  - i. Glibenclamide 2.5-10 mg  $\rightarrow$  metformin 850 mg + glibenclamide current dose
  - ii. Glibenclamide 15-20 mg  $\rightarrow$  metformin 850 mg + glibenclamide 10 mg
  - b. Refuses to take metformin
    - i. Glibenclamide 2.5 mg  $\rightarrow$  glibenclamide 5 mg
    - ii. Glibenclamide 5 mg  $\rightarrow$  glibenclamide 10 mg
- iii. Glibenclamide 10-20 mg  $\rightarrow$  glibenclamide 10 mg
- 9. Taking glibenclamide with hypoglycemia or hypoglycemia symptoms
  - a. Glibenclamide 2.5 mg  $\rightarrow$  metformin 1700 mg
  - b. Glibenclamide 5 mg  $\rightarrow$  metformin 1700 mg + glibenclamide 2.5 mg
  - c. Glibenclamide 10 mg  $\rightarrow$  metformin 1700 mg + glibenclamide 5 mg
  - d. Glibenclamide 15-20 mg  $\rightarrow$  metformin 1700 mg + glibenclamide 10 mg
- 10. Taking glibenclamide with hypoglycemia or hypoglycemia symptoms, previous problems with metformin
  - a. Agrees to take metformin
    - i. Glibenclamide 2.5 mg  $\rightarrow$  metformin 850 mg
    - ii. Glibenclamide 5 mg  $\rightarrow$  metformin 850 mg + glibenclamide 2.5 mg
    - iii. Glibenclamide 10 mg  $\rightarrow$  metformin 850 mg + glibenclamide 5 mg
    - iv. Glibenclamide 15-20 mg  $\rightarrow$  metformin 850 mg + glibenclamide 10 mg
  - b. Refuses to take metformin
    - i. Glibenclamide 2.5 mg  $\rightarrow$  MD consult
    - ii. Glibenclamide 5 mg  $\rightarrow$  glibenclamide 2.5 mg
    - iii. Glibenclamide 10 mg  $\rightarrow$  glibenclamide 5 mg
    - iv. Glibenclamide 15-20 mg  $\rightarrow$  glibenclamide 10 mg
- 11. Taking metformin and glibenclamide without problems
  - a. Metformin 500-1000 mg + glibenclamide 2.5-10 mg  $\rightarrow$  metformin 1700 mg + current glibenclamide dose
  - b. Metformin 500-1000 mg + glibenclamide 15-20 mg  $\rightarrow$  metformin 1700 mg + glibenclamide 10 mg
  - c. Metformin 1500-2000 mg + glibenclamide 2.5-10 mg  $\rightarrow$  metformin 2550 mg + glibenclamide current dose
  - d. Metformin 1500-2000 mg + glibenclamide 15-20 mg  $\rightarrow$  metformin 2550 mg + glibenclamide 10 mg
  - e. Metformin 2550 mg + glibenclamide 2.5 mg  $\rightarrow$  metformin 2550 mg + glibenclamide 5 mg
  - f. Metformin 2550 mg + glibenclamide 5 mg → metformin 2550 mg + glibenclamide 10 mg

g. Metformin 2550 mg + glibenclamide 10-20 mg → metformin 2550 mg + glibenclamide 10 mg

12. Taking metformin and glibenclamide, problems with metformin

- a. Agrees to take metformin
  - i. Metformin 500-850 mg + glibenclamide 2.5 mg  $\rightarrow$  metformin 850 mg + glibenclamide 5 mg
  - ii. Metformin 500-850 mg + glibenclamide 5 mg  $\rightarrow$  metformin 850 mg + glibenclamide 10 mg

#### [name]

- iii. Metformin 500-850 mg + glibenclamide 10-20 mg  $\rightarrow$  metformin 850 mg + glibenclamide 10 mg
- b. Refuses to take metformin
  - i. Metformin 500-850 mg + glibenclamide 2.5 mg  $\rightarrow$  glibenclamide 5 mg
  - ii. Metformin 500-850 mg + glibenclamide 5 mg  $\rightarrow$  glibenclamide 10 mg
  - iii. Metformin 500-850 mg + glibenclamide 10-20 mg  $\rightarrow$  glibenclamide 10 mg
- c. Metformin 1000-1700 mg + glibenclamide 2.5 mg  $\rightarrow$  metformin 850 mg + glibenclamide 5 mg
- d. Metformin 1000-1700 mg + glibenclamide 5 mg  $\rightarrow$  metformin 850 mg + glibenclamide 10 mg
- e. Metformin 1000-1700 mg + glibenclamide 10-20 mg → metformin 850 mg + glibenclamide 10 mg
- f. Metformin 2000-2550 mg + glibenclamide 2.5 mg → metformin 1700 mg + glibenclamide 5 mg
- g. Metformin 2000-2550 mg + glibenclamide 5 mg→ metformin 1700 mg + glibenclamide 10 mg
- h. Metformin 2000-2550 mg + glibenclamide 10-20 mg → metformin 1700 mg + glibenclamide 10 mg

13. Taking metformin and glibenclamide with hypoglycemia or hypoglycemia symptoms

- a. Metformin 500-1000 mg + glibenclamide 2.5 mg → metformin 1700 mg
- b. Metformin 500-1000 mg + glibenclamide 5 mg  $\rightarrow$  metformin 1700 mg + glibenclamide 2.5 mg
- c. Metformin 500-1000 mg + glibenclamide 10 mg  $\rightarrow$  metformin 1700 mg + glibenclamide 5 mg
- d. Metformin 500-1000 mg + glibenclamide 15-20 mg → metformin 1700 mg + glibenclamide 10 mg
- e. Metformin 1500-2000 mg + glibenclamide 2.5 mg → metformin 2550 mg
- f. Metformin 1500-2000 mg + glibenclamide 5 mg → metformin 2550 mg + glibenclamide 2.5 mg
- g. Metformin 1500-2000 mg + glibenclamide 10 mg  $\rightarrow$  metformin 2550 mg + glibenclamide 5 mg
- h. Metformin 1500-2000 mg + glibenclamide 15-20 mg → metformin 2550 mg + glibenclamide 10 mg
- i. Metformin 2550 mg + glibenclamide 2.5 mg  $\rightarrow$  metformin 2550 mg
- j. Metformin 2550 mg + glibenclamide 5 mg → metformin 2550 mg + glibenclamide 2.5 mg
- k. Metformin 2550 mg + glibenclamide 10 mg  $\rightarrow$  metformin 2550 mg + glibenclamide 5 mg
- I. Metformin 2550 mg + glibenclamide 15-20 mg → metformin 2550 mg + glibenclamide 10 mg

14. Taking metformin and glibenclamide, with hypoglycemia or hypoglycemia symptoms, problems with metformin

- a. Agrees to take metformin
  - i. Metformin 500-850 mg + glibenclamide 2.5 mg  $\rightarrow$  metformin 850 mg
  - ii. Metformin 500-850 mg + glibenclamide 5 mg  $\rightarrow$  metformin 850 mg + glibenclamide 2.5 mg
  - iii. Metformin 500-850 mg + glibenclamide 10 mg  $\rightarrow$  metformin 850 mg + glibenclamide 5 mg
  - iv. Metformin 500-850 mg + glibenclamide 15-20 mg → metformin 850 mg + glibenclamide 10 mg
- b. Refuses to take metformin
  - i. Metformin 500-850 mg + glibenclamide 2.5 mg  $\rightarrow$  MD consult
  - ii. Metformin 500-850 mg + glibenclamide 5 mg  $\rightarrow$  glibenclamide 2.5 mg
  - iii. Metformin 500-850 mg + glibenclamide 10 mg  $\rightarrow$  glibenclamide 5 mg
  - iv. Metformin 500-850 mg + glibenclamide 15-20 mg  $\rightarrow$  glibenclamide 10 mg
- c. Metformin 1000-1700 mg + glibenclamide 2.5 mg  $\rightarrow$  metformin 850 mg
- d. Metformin 1000-1700 mg + glibenclamide 5 mg  $\rightarrow$  metformin 850 mg + glibenclamide 2.5 mg
- e. Metformin 1000-1700 mg + glibenclamide 10 mg  $\rightarrow$  metformin 850 mg + glibenclamide 5 mg
- f. Metformin 1000-1700 mg + glibenclamide 15-20 mg → metformin 850 mg + glibenclamide 10 mg
- g. Metformin 2000-2550 mg + glibenclamide 2.5 mg → metformin 1700 mg

Version #: 1.0

#### [name]

- h. Metformin 2000-2550 mg + glibenclamide 5 mg  $\rightarrow$  metformin 1700 mg + glibenclamide 2.5 mg
- i. Metformin 2000-2550 mg + glibenclamide 10 mg  $\rightarrow$  metformin 1700 mg + glibenclamide 5 mg
- j. Metformin 2000-2550 mg + glibenclamide 15-20 mg  $\rightarrow$  metformin 1700 mg + glibenclamide 10 mg

#### 9≤ A1c ≤14

- 1. Not taking medications  $\rightarrow$  metformin 1700 mg + glibenclamide 2.5 mg
- 2. Not taking medications, problems with metformin
  - a. Agrees to take metformin → metformin 850 mg + glibenclamide 2.5 mg
  - b. Refuses to take metformin  $\rightarrow$  glibenclamide 2.5 mg
- 3. Not taking medications, hypoglycemia or hypoglycemia symptoms  $\rightarrow$  metformin 1700 mg
- 4. Not taking medications, hypoglycemia or hypoglycemia symptoms, problems with metformin
  - a. Agrees to take metformin, prescribed glibenclamide >2.5 mg  $\rightarrow$  metformin 850 mg + glibenclamide 2.5 mg
  - b. Agrees to take metformin, prescribed glibenclamide 2.5 mg  $\rightarrow$  metformin 850 mg
  - c. Refuses to take metformin, prescribed glibenclamide >2.5 mg  $\rightarrow$  glibenclamide 2.5 mg
  - d. Refuses to take metformin, prescribed glibenclamide 2.5 mg  $\rightarrow$  MD consult
- 5. Taking metformin without problems
  - a. Metformin 500-2000 mg  $\rightarrow$  metformin 1700 mg + glibenclamide 2.5 mg
  - b. Metformin 2550 mg  $\rightarrow$  metformin 2550 mg + glibenclamide 2.5 mg
- 6. Taking metformin with problems
  - a. Metformin 500-850 mg, agrees to take metformin  $\rightarrow$  metformin 850 mg + glibenclamide 2.5 mg
  - b. Metformin 500-850 mg, refuses to take metformin  $\rightarrow$  glibenclamide 2.5 mg
  - c. Metformin 1000-1700 mg  $\rightarrow$  metformin 850 mg + glibenclamide 2.5 mg
  - d. Metformin 2000-2550 mg  $\rightarrow$  metformin 1700 mg + glibenclamide 2.5 mg
- 7. Taking glibenclamide without problems
  - a. Glibenclamide 2.5-10 mg → metformin 1700 mg +glibenclamide current dose
  - b. Glibenclamide 15-20 mg  $\rightarrow$  metformin 1700 mg + glibenclamide 10 mg
- 8. Taking glibenclamide without problems, previous problems with metformin
  - a. Agrees to take metformin
    - i. Glibenclamide 2.5-10 mg → metformin 850 mg + glibenclamide current dose
    - ii. Glibenclamide 15-20 mg  $\rightarrow$  metformin 850 mg + glibenclamide 10 mg
  - b. Refuses to take metformin
    - i. Glibenclamide 2.5 mg  $\rightarrow$  glibenclamide 5 mg
    - ii. Glibenclamide 5 mg  $\rightarrow$  glibenclamide 10 mg
    - iii. Glibenclamide 10-20 mg  $\rightarrow$  glibenclamide 10 mg
- 9. Taking glibenclamide with hypoglycemia or hypoglycemia symptoms
  - a. Glibenclamide 2.5 mg  $\rightarrow$  metformin 1700 mg
    - b. Glibenclamide 5 mg  $\rightarrow$  metformin 1700 mg + glibenclamide 2.5 mg
    - c. Glibenclamide 10 mg  $\rightarrow$  metformin 1700 mg + glibenclamide 5 mg
    - d. Glibenclamide 15-20 mg  $\rightarrow$  metformin 1700 mg + glibenclamide 10 mg
- 10. Taking glibenclamide with hypoglycemia or hypoglycemia symptoms, previous problems with metformin a. Agrees to take metformin
  - i. Glibenclamide 2.5 mg  $\rightarrow$  metformin 850 mg
    - ii. Glibenclamide 5 mg  $\rightarrow$  metformin 850 mg + glibenclamide 2.5 mg
    - iii. Glibenclamide 10 mg  $\rightarrow$  metformin 850 mg + glibenclamide 5 mg
    - iv. Glibenclamide 15-20 mg  $\rightarrow$  metformin 850 mg + glibenclamide 10 mg
- Version #: 1.0

[name]

- b. Refuses to take metformin
  - i. Glibenclamide 2.5 mg  $\rightarrow$  MD consult
  - ii. Glibenclamide 5 mg  $\rightarrow$  glibenclamide 2.5 mg
  - iii. Glibenclamide 10 mg  $\rightarrow$  glibenclamide 5 mg
  - iv. Glibenclamide 15-20 mg  $\rightarrow$  glibenclamide 10 mg
- 11. Taking metformin and glibenclamide without problems
  - a. Metformin 500-1000 mg + glibenclamide 2.5-10 mg → metformin 1700 mg + current glibenclamide dose
  - b. Metformin 500-1000 mg + glibenclamide 15-20 mg → metformin 1700 mg + glibenclamide 10 mg
  - c. Metformin 1500-2000 mg + glibenclamide 2.5-10 mg  $\rightarrow$  metformin 2550 mg + glibenclamide current dose
  - d. Metformin 1500-2000 mg + glibenclamide 15-20 mg  $\rightarrow$  metformin 2550 mg + glibenclamide current dose
  - e. Metformin 2550 mg + glibenclamide 2.5-10 mg → metformin 2550 mg + glibenclamide current dose
  - f. Metformin 2550 mg + glibenclamide 15-20 mg  $\rightarrow$  metformin 2550 mg + glibenclamide 10 mg
- 12. Taking metformin and glibenclamide, problems with metformin
  - a. Agrees to take metformin
    - i. Metformin 500-850 mg + glibenclamide 2.5 mg  $\rightarrow$  metformin 850 mg + glibenclamide 5 mg
    - ii. Metformin 500-850 mg + glibenclamide 5 mg  $\rightarrow$  metformin 850 mg + glibenclamide 10 mg
    - iii. Metformin 500-850 mg + glibenclamide 10-20 mg → metformin 850 mg + glibenclamide 10 mg
  - b. Refuses to take metformin
    - i. Metformin 500-850 mg + glibenclamide 2.5 mg  $\rightarrow$  glibenclamide 5 mg
    - ii. Metformin 500-850 mg + glibenclamide 5 mg  $\rightarrow$  glibenclamide 10 mg
    - iii. Metformin 500-850 mg + glibenclamide 10-20 mg  $\rightarrow$  glibenclamide 10 mg
  - c. Metformin 1000-1700 mg + glibenclamide 2.5 mg  $\rightarrow$  metformin 850 mg + glibenclamide 5 mg
  - d. Metformin 1000-1700 mg + glibenclamide 5 mg  $\rightarrow$  metformin 850 mg + glibenclamide 10 mg
  - e. Metformin 1000-1700 mg + glibenclamide 10-20 mg → metformin 850 mg + glibenclamide 10 mg
  - f. Metformin 2000-2550 mg + glibenclamide 2.5 mg  $\rightarrow$  metformin 1700 mg + glibenclamide 5 mg
  - g. Metformin 2000-2550 mg + glibenclamide 5 mg→ metformin 1700 mg + glibenclamide 10 mg
  - Metformin 2000-2550 mg + glibenclamide 10-20 mg → metformin 1700 mg + glibenclamide 10 mg
- 13. Taking metformin and glibenclamide with hypoglycemia or hypoglycemia symptoms
  - a. Metformin 500-1000 mg + glibenclamide 2.5 mg  $\rightarrow$  metformin 1700 mg
  - b. Metformin 500-1000 mg + glibenclamide 5 mg  $\rightarrow$  metformin 1700 mg + glibenclamide 2.5 mg
  - c. Metformin 500-1000 mg + glibenclamide 10 mg  $\rightarrow$  metformin 1700 mg + glibenclamide 5 mg
  - d. Metformin 500-1000 mg + glibenclamide 15-20 mg → metformin 1700 mg + glibenclamide 10 mg
  - e. Metformin 1500-2000 mg + glibenclamide 2.5 mg → metformin 2550 mg
  - f. Metformin 1500-2000 mg + glibenclamide 5 mg  $\rightarrow$  metformin 2550 mg + glibenclamide 2.5 mg
  - g. Metformin 1500-2000 mg + glibenclamide 10 mg → metformin 2550 mg + glibenclamide 5 mg
  - h. Metformin 1500-2000 mg + glibenclamide 15-20 mg → metformin 2550 mg + glibenclamide 10 mg
  - i. Metformin 2550 mg + glibenclamide 2.5 mg  $\rightarrow$  metformin 2550 mg
  - j. Metformin 2550 mg + glibenclamide 5 mg → metformin 2550 mg + glibenclamide 2.5 mg

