## 2.6 Dose Rationale

The standard doses for metformin and glibenclamide used in our program are as follows:

- Metformin: 850 mg, 1500 mg, or 2550 mg per day (850 mg dosed once, twice, or three times daily, respectively)
- Glibenclamide: 2.5 mg, 5 mg, or 10 mg one time daily

In accordance with diabetes treatment guidelines, metformin is the first line medication for all patients in the program and is continued in all patients as long as it is tolerated and there are no contraindications. The standard starting dose of metformin in our protocol is 1700 mg (850 mg twice daily) as 1500 - 2000 mg is thought to be the usual effective dose range.

Also in accordance with ADA and AACE guidelines, patients with initial or repeat A1c ≥9% are placed on dual therapy with metformin and glibenclamide. For patients who are initially started on metformin alone and whose A1c is <9%, glibenclamide is added if they are not meeting glycemic targets despite maximum daily dose of metformin (2550 mg). Though the maximum dose of glibenclamide is 20 mg, most of the hypoglycemic effect of glibenclamide is thought to come at the initial 2.5 mg dose and doses above 10 mg per day are not thought to provide significant additional benefit. For this reason, the maximal dose of glibenclamide used in our program is 10 mg per day.

Glibenclamide does carry a higher risk of hypoglycemia compared to newer sulfonylureas such as glimepiride and glipizide. However, glibenclamide was selected for use in this program because other sulfonylureas are either not readily available in Guatemala or are prohibitively expensive compared to glibenclamide. In addition, though glibenclamide carries a higher hypoglycemia risk than other sulfonylureas, the risk of serious 15

[name]

hypoglycemia (requiring the assistance of another person or hospitalization) is still low, with reported occurrence in only 0.5% of patients in a meta-analysis of sulfonylurea studies.

The application will recommend aspirin for patients with a history of ischemic stroke and CAD to prevent recurrent events and for patients with possible ACS, as long as contraindications are not present. The dose used for ASCVD prevention is 81 mg per day, which is in accordance with current consensus guidelines. The dosage used for treatment of possible ACS is 324 mg, also in accordance with current consensus guidelines.

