# 6.5 Starting Dose and Dose Escalation Schedule

Metformin will be started at 850 mg once daily and increased to the target dose of 1700 mg after 2 weeks. If not meeting treatment goals after ≥1 month, metformin can be increased to 2550 mg. Patients who are unable to tolerate the 1700 mg dose will take the 850 mg dose.

Version #: 1.0

[name]

Glibenclamide will be used for patients who are unable to tolerate metformin, in addition to metformin if A1c  $\geq$ 9, or if glycemic goals not met despite maximal dose of metformin. Dosing will start at 2.5 mg once per day. If glycemic goals are not met after  $\geq$ 1 month, dose will be escalated to 5 mg once per day and then 10 mg once per day as needed.

Aspirin will be dosed at 81 mg once per day for secondary prevention in eligible patients with history of MI or stroke or patients who have new chest pain and are awaiting medical workup for possible CAD. Patients with high risk chest pain and possible ACS will be treated with aspirin 324 mg (four 81 mg tablets) once while awaiting emergency transport to SLMH.

Please consult Appendix 8, Appendix 10, and Appendix 11 for further information on medication titration protocols

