#### FBG <80 (<90) or PPBG<130(150)

- 1. Metformin without problems, adherent  $\rightarrow$  continue current doses
- 2. Metformin without problems, nonadherent
  - a. Metformin 850 mg  $\rightarrow$  metformin 850 mg
  - b. Metformin 1700-2550 mg → metformin 1700 mg
- 3. Metformin with problems, adherent
  - a. Metformin 850 mg, willing to continue  $\rightarrow$  Metformin 850 mg
  - b. Metformin 850 mg, not willing to continue  $\rightarrow$  stop medications, check A1c when next indicated
  - c. Metformin 1700 mg  $\rightarrow$  metformin 850 mg
  - d. Metformin 2550 mg  $\rightarrow$  metformin 1700 mg
- 4. Metformin with problems, nonadherent  $\rightarrow$  same as #3
- Glibenclamide without problems, no previous problems with metformin, took yesterday → metformin 1700 mg
- Glibenclamide without problems, no previous problems with metformin, did not take yesterday → metformin 1700 mg
- 7. Glibenclamide without problems, previous problems with metformin, took yesterday
  - a. Agrees to take metformin
    - i. Glibenclamide 2.5-5 mg  $\rightarrow$  metformin 850 mg
    - ii. Glibenclamide 10 mg → metformin 850 mg + glibenclamide 2.5 mg
  - b. Refuses to take metformin
    - i. Glibenclamide 2.5 mg  $\rightarrow$  stop medications, recheck A1c in 3 months
    - ii. Glibenclamide 5 mg  $\rightarrow$  glibenclamide 2.5 mg
    - iii. Glibenclamide 10 mg  $\rightarrow$  glibenclamide 5 mg
- 8. Glibenclamide without problems, previous problems with metformin, did not take yesterday
  - a. Agrees to take metformin  $\rightarrow$  metformin 850 mg
  - b. Refuses to take metformin  $\rightarrow$  stop medications, recheck A1c in 3 months
- Glibenclamide with hypoglycemia or hypoglycemia symptoms, no previous problems with metformin, took vesterday → metformin 1700 mg
- 10. Glibenclamide with hypoglycemia or hypoglycemia symptoms, no previous problems with metformin, did not take yesterday → metformin 1700 mg
- Glibenclamide with hypoglycemia or hypoglycemia symptoms, previous problems with metformin, took yesterday → same as #8
- Glibenclamide with hypoglycemia or hypoglycemia symptoms, previous problems with metformin did not take yesterday → same as #8
- 13. Metformin and glibenclamide without problems, adherent, took glibenclamide yesterday
  - a. Metformin 850 mg + glibenclamide any dose  $\rightarrow$  metformin 1700 mg
  - b. Metformin 1700-2550 mg + glibenclamide 2.5 mg  $\rightarrow$  metformin 1700 mg

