  - c. Metformin 1700-2550 mg + glibenclamide 5 mg  $\rightarrow$  metformin 1700 mg + glibenclamide 2.5 mg
  - d. Metformin 1700-2550 mg + glibenclamide 10 mg  $\rightarrow$  metformin 1700 mg + glibenclamide 5 mg
- 14. Metformin and glibenclamide without problems, nonadherent, took glibenclamide yesterday  $\rightarrow$  same as #13
- 15. Metformin and glibenclamide without problems, adherent, did not take glibenclamide yesterday  $\rightarrow$  metformin 1700 mg

<sup>18 Numbers in parentheses refer to the relevant measurements for patients who have relaxed glycemic goals (A1c ≤8, FBG 90-150, PPBG <200)

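### Appendix 8, A1c 9-14: enrollment row 11d keeps glibenclamide at 15-20 mg against the program's 10 mg maximum; row 11e, a lesser matter, holds doses that the lower A1c band raises

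*Combined protocol and SAP*

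**What the plan says.** Section 2.6 (Dose Rationale) states that "the maximal dose of glibenclamide used in our program is 10 mg per day". Its reason is that "doses above 10 mg per day are not thought to provide significant additional benefit"; the same section gives 20 mg as the drug's own maximum. Section 6.5 describes stepwise titration: if goals are not met after at least one month, the "dose will be escalated to 5 mg once per day and then 10 mg once per day as needed".

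Appendix 8 turns this into enrollment rules by A1c band. Row 11 of the 9≤ A1c ≤14 band covers patients taking metformin and glibenclamide without problems:

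- Row 11d has the input "Metformin 1500-2000 mg + glibenclamide 15-20 mg". Its output is metformin 2550 mg with the current glibenclamide dose.
- Row 11e reads "Metformin 2550 mg + glibenclamide 2.5-10 mg → metformin 2550 mg + glibenclamide current" dose.
- Rows 11b and 11f, also for 15-20 mg of glibenclamide, both cut to 10 mg.

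The next lower band (above treatment goal, below 9) cuts 15-20 mg to 10 mg in its own row 11d. In rows 11e-f it raises 2.5 mg to 5 mg and 5 mg to 10 mg on metformin 2550 mg; its row 11f is "Metformin 2550 mg + glibenclamide 5 mg → metformin 2550 mg + glibenclamide 10 mg".

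Follow-up dosing is in Appendix 10 (monthly, by glucose) and Appendix 11 (month 3, by A1c). Wherever Appendix 10 names a glibenclamide dose, it is 2.5, 5 or 10 mg. Appendix 9 gives patient instructions for those three doses only.

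**The concern.** Section 2.7.1 identifies glibenclamide as the study drug most likely to cause harm, and community health workers dispense on the application's recommendation before any physician sees it. A rule that exceeds the plan's own cap is therefore a dosing-safety matter, even in a small cell.

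The follow-up tables also assume that the cap has held. Section 2.7.2 promises down-titration when hypoglycemia symptoms are present, and Appendix 4 says the application will lower the dose. For a patient on 15-20 mg, many of the rows that would do this do not exist.

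Row 11e raises a question of consistency: the same regimen is intensified less at a higher A1c, and no reason is given.

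**Working it through.** No power or sample-size figure is involved. The check compares tables and counts rules.

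**1. Row 11d against the cap.** Cap 10 mg (section 2.6); row 11d output 15-20 mg. 15/10 = 150% and 20/10 = 200%.

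**2. Is it isolated?** Appendix 8 rules with a named glibenclamide input in the 15-20 mg range (15, 20, 15-20 or 10-20 mg):

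| A1c band | Rules | Output ≤10 mg |
|---|---|---|
| 6.5 to goal | 18 | 18 |
| Above goal, below 9 | 20 | 20 |
| 9 to 14 | 20 | 19 |
| Total | 58 | 57 |

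The exception is row 11d.

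**3. What the monthly table does with the output.** I took metformin 2550 mg with glibenclamide 15-20 mg through Appendix 10 rows 13-28, the 16 dual-therapy situations, in each of the four glucose bands with their own table (16 × 4 = 64). A row matches if it names the dose, covers any dose, continues current doses, or gives a fixed regimen.

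| Band (stricter FBG limits) | No match | Continues above 10 mg | Stops glibenclamide |
|---|---|---|---|
| FBG <80 | 8 | 0 | 8 |
| 80-130 | 9 | 3 | 4 |
| 130-180 | 11 | 5 | 0 |
| 180-400 | 10 | 6 | 0 |
| Total | 38 | 14 | 12 |

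38 + 14 + 12 = 64. As an example, row 13 of the lowest band, "Metformin and glibenclamide without problems, adherent, took glibenclamide yesterday", has "Metformin 1700-2550 mg + glibenclamide 10 mg" as its highest input, so 15-20 mg has no entry.

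**4. Hypoglycemia symptoms (rows 21-28).** No match: 4 + 4 + 8 + 8 = 24 of 32; the other 8 stop glibenclamide. For patients who took glibenclamide the day before (rows 21, 22, 25, 26), none of the 4 × 4 = 16 situations matches.

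**5. Month 3.** The same trace through Appendix 11 rows 13-20 in four A1c bands (8 × 4 = 32): no match 2 + 6 + 6 + 6 = 20; continues above 10 mg 0 + 2 + 2 + 2 = 6; stops 6 + 0 + 0 + 0 = 6.

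**6. After correction.** With row 11d set to 10 mg, every previously unmatched situation in Appendices 10 and 11 has an entry for metformin 2550 mg with glibenclamide 10 mg.

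**7. Row 11 of the two bands compared.** Three metformin ranges × five glibenclamide doses (2.5, 5, 10, 15, 20 mg) = 15 cells:

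- 2 above the cap: metformin 1500-2000 mg with 15 or 20 mg (row 11d).
- 2 inverted: on metformin 2550 mg, 2.5 mg goes to 5 mg at A1c 8.9 but stays 2.5 mg at 9.0; 5 mg goes to 10 mg at 8.9 but stays 5 mg at 9.0 (row 11e).
- 11 identical, including 10 mg on metformin 2550 mg, which both bands hold.

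Neither enrollment row carries a glucose or adherence condition that could explain the inversion. Appendix 11, A1c 9-14, rows 13c-d raise the same two regimens for adherent patients with glucose above goal.

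**The case against.** Several points on the other side are sound.

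- Row 11d starts no drug and does not raise glibenclamide. It applies to patients already taking 15-20 mg without problems, within the 20 mg drug maximum. It looks like a copying slip from row 11c. All of this stands and limits the harm; it does not make the output consistent with section 2.6.
- The medical director reviews each visit within one week and has changes passed on in that week (Physician Oversight), before a month-1 visit that may vary by one week either way. The gap in Appendix 10 therefore arises only if that review misses or accepts the dose. This stands, and the conclusion is conditional on it. The review does, however, follow the first dispensing.
- Section 2.1 provides telephone advice for situations outside the protocols, section 2.7.2 plans scenario testing, and section 9.4 mentions range and consistency checks. These may catch the error. But row 11d gives a definite answer, so it prompts no call, and testing against the printed table would pass it. The application code is not in the documents, so its actual output is unknown.
- On row 11e, section 6.5 escalates only after at least one month, so it does not require an increase at enrollment. Appendix 10 row 13c-d (FBG at least 180(200) or PPBG at least 300, adherent, dose taken the day before) or month 3 can raise the dose later. This stands: the effect is a delay in the cautious direction.

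A reader might infer that the monthly table has no rows at all for the row 11d patient. It has: 14 + 12 = 26 of 64 situations match, although 14 of those carry on above the cap.

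A reader might also infer that rows 1-4 of this band, which mention only patients not taking medication, send nonadherent patients into rows that raise glibenclamide. The documents do not establish that. The branches on prescribed glibenclamide in row 4 suggest nonadherent patients were meant to be there. It is an unclear label.

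**Conclusion.** Row 11d is wrong as written: 15-20 mg against a 10 mg maximum, one rule in 58, contradicted by its neighbors 11b and 11f and by row 11d of the lower band. If uncorrected at the one-week review, it leaves 38 of 64 monthly dual-therapy situations without a rule, including all 16 with hypoglycemia symptoms and glibenclamide taken the day before.

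Row 11e is a real but secondary inconsistency, confined to 2.5 and 5 mg on metformin 2550 mg. Its consequence is delayed intensification. Rows 1-4 need only a clarification.

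The cell counts are unweighted. The documents do not say how many patients would fall in any cell, and the effect on mean A1c is probably small. The case rests on dosing safety and internal consistency, and assumes that the application follows the printed tables. It gives no ground for saying that the primary comparison is biased.

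**What to change.** 1. Row 11d, A1c 9-14: change the output to metformin 2550 mg with glibenclamide 10 mg.
2. Row 11e, subject to the medical director's confirmation: on metformin 2550 mg, raise 2.5 mg to 5 mg and 5 mg to 10 mg, and leave 10 mg unchanged. If the present rule is intended, state the reason.
3. Rows 1-4: add nonadherent patients to the label, as in the lower bands.
4. Add an automated check to the application build that no output exceeds glibenclamide 10 mg. A wider audit across Appendices 8, 10 and 11 for missing rows or inversions is optional.

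The cost is one table correction and an application rebuild before enrollment, with no extra visits, tests or patients.
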